# 2.2.2 Secondary Objectives

The secondary objectives of the study are as follows:

- To compare efficacy of Eziclen®/Izinova® versus Klean-Prep® on overall and segmental cleansing and colonoscopy quality indicators
- To assess compliance with preparation administration in both study arms
- To compare safety, acceptability and tolerability of Eziclen®/Izinova® versus Klean-Prep®

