- Urine analysis by dipstick (pH, protein, ketones, bilirubin, blood, urobilinogen, nitrites, leukocytes, glucose and specific gravity, urine microscopic examination
- Blood and urinary samples for sulphate measurement
- Blood pregnancy test, if female of child-bearing potential. Urine pregnancy test will be performed only when blood tests including pregnancy have been performed prior to Visit 1.
- Indication(s) for colonoscopy to be collected
- Randomisation
- Drug accountability, study treatment dispensation by study nurse (with explanation of treatment administration)
- Subject/caregiver questionnaires dispensation by study nurse (with explanation of questionnaires including compliance measurement)
- Prior and concomitant medications including supplements, herbal medications and nonprescribed compounds
- Prior and concomitant non-drug therapies and surgical procedures
- Collection of AEs from the time of informed consent signature
- Subject status at the end of the visit

Records up to the time of premature termination should be completed. In the event that the subject was not receiving IMP, the primary reason will be recorded.

If any Visit 1 serum chemistry result is considered abnormal and clinically significant by the investigator result may be checked per investigator's decision. The abnormal significant result will be reported as an AE.

In case of non-inclusion of the subject, the primary reason will be recorded.

Following confirmation of eligibility for the study, subjects will be given a randomisation/treatment allocation number and allocated to one of the dosing groups specified in Section 6.1.

Caregivers and subjects will be provided with a subject leaflet containing instructions on how to administer the study preparation. Caregivers will be provided with a Treatment Acceptability Questionnaire (see Section 7.3.2.3) to report their child's experience with the study preparation, and a Symptom Scale to rate subject tolerability (see Section 8.6). Subjects/caregivers will complete these questionnaires during and after the treatment administration.

Subjects will be hospitalised for preparation. The treatment will be prepared by a nurse and administration will be monitored as described in Section 3.4. The nurse or caregiver will fill in

PAGE 42/103

the questionnaires or ensure that the subject fills in, as appropriate. If a subject is unable to complete the preparation, a nasogastric tube will be placed.

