The bowel cleansing preparation will be taken orally on the evening of the day before colonoscopy.

The following procedures will be performed during and after treatment administration:

- Treatment preparation taken by subject (nasogastric tube may be placed if needed for completion of preparation)
- Completion of subject leaflet (for Eziclen®/Izinova® or Klean-Prep® depending on allocated treatment arm) which contains:
  - o Treatment administration, compliance, Treatment Acceptability Questionnaires and Symptom Scale by subject/caregiver
  - o Information about bowel movement and stool
  - o Time of first clear watery stool

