# Approximately 2 hours after the start of drinking the first portion (e.g., 8:00 pm):

The second 375 mL portion of the Eziclen®/Izinova® preparation will be drunk slowly in ½ to 1 hour followed by additional 750 mL of water over the next hour. The total ingested volume is 1125 mL.

The total volume of preparation drunk is 750 mL, with an additional 1500 mL of water, for a total of 2250 mL. If a subject experiences difficulty in drinking the bowel cleansing preparation, a nasogastric tube will be placed, the rate of administration should not exceed 30 mL/kg/hour.

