# 7.3.2.2 Treatment/Compliance

The treatment questionnaire will be completed by the caregiver or subject after the subject completes each dose of preparation. The subject/caregiver will provide information about treatment preparation, residual volumes of preparation (volumes not taken by the subject) and start and stop times of intake. For the Eziclen®/Izinova® treatment only, information about the residual volume of water will be reported.

PAGE 48/103

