proc mixed data= ADEX(where=(EXCAT='COMPLIANCE' and EXSCAT='Overall' and ITTFL='Y'));

class TRTP COUNTRYC SUBGROUP;

model COMPLIPCT = TRTP COUNTRYC SUBGROUP TRTP*SUBGROUP; lsmeans TRTP*SUBGROUP / diff cl;

run;

Additionally, a subject will be considered as compliant with the instructions of use provided in the prescription if he/she drinks the whole preparation (volume = 100 %). The proportion of subjects compliant with the instructions of use provided in the prescription will be presented using summary statistics with the 95 % CI by treatment group and analysed using Cochran-Mantel-Hænszel (CMH) chi-square for the proportions adjusting for country effect. The general association statistic will be used to assess the test significance.

The SAS Freq procedure will be used as follows:

```
proc freq data=ADEX(where=(EXCAT='COMPLIANCE' and EXSCAT='Overall' and ITTFL='Y'));
```

table COUNTRYC*TRTP*COMPLI / CMH; by ASPID;

run;

The difference of proportions with the 95 % CI and p-value will be summarised.

Finally, the compliance will be presented by categories (100 %,]100-75],]75-50] and < 50 %). The proportion of subjects in each category will be presented using summary statistics with the 95 % CI by treatment group and analysed using Cochran-Mantel-Hænszel (CMH) chi-square for the proportions adjusting for country effect. The row mean scores differ statistic will be used to assess the test significance.

The SAS Freq procedure will be used as follows:

proc freq data=ADEX(where=(EXCAT='COMPLIANCE' and EXSCAT='Overall' and ITTFL='Y')); table COUNTRYC*TRTP*COMPLICL / CMH; by ASPID;

run;

The difference of proportions with the 95 % CI and p-value will be summarised.

The percentage of compliance, the proportion of patients considered as compliant and the compliance in categories will be described after each dose and overall. For the Eziclen/Izinova treatment group, the compliance will be also described separately for active treatment and hydration after each dose and overall.

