3.2.2.4 Tolerability

Tolerability will be collected using a Symptom Scale after each dose of treatment for stomach cramping, stomach bloating and nausea on a paediatric 5-point scale (with 1=no symptom, 2=mild, 3=bothersome, 4=distressing and 5=severely distressing symptoms).

Each symptom after each dose will be described by treatment group using a frequency table. Additionally, each symptom after each dose will be summarised by treatment group as well as the total score (sum of the three symptoms).

Finally, each symptom after each dose will be summarised by treatment group and use of nasogastric tube (Yes/No), as well as sex, age class and weight class.

3.2.2.5 *Physical examination*

A listing with the date of examination and the status of the examination (performed/not performed) will be provided by treatment group, subject and examination date.

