Appendix 1 Derived data

The following derived data will be calculated:

(1) Treatment group

Treatment groups will be defined as "Eziclen/Izinova" and "Klean-Prep".

(2) Study duration

Study duration (days) will be calculated as (last visit attended - date of informed consent) + 1.

- (3) Successful treatment preparation
- A successful preparation will be derived from a colon cleansing scored as excellent (4) or good (3).
- A failure preparation will be defined as:
 - Fair (2) or poor (1) according to colon cleansing score,
 - Any subject who did not have a colonoscopy based on the investigator's assessment of the cleansing (insufficient faecal output, unclear faecal discharge, etc.) or due to preparation related AEs,
 - Any subject for whom cleaning was not adequate for evaluation,
 - Any subject for whom rescue treatment (saline enema) was needed.

(4) Time to clear effluent

It is defined as the time (expressed in hours) from the first intake of prescription to the first clear watery stool occurrence if any, or to the time of colonoscope introduction, if no clear watery stool is observed before the beginning of the procedure and then the time will be considered as censored for the survival analysis. See section 3.2.1.2.3.

(5) Completion of the procedure

"Yes" if the colonoscopy reached the caecum and the item "Was physician able to reach the caecum?" is "Yes", "No" otherwise.

(6) Duration of the intubation

It is defined as the time (expressed in minutes) from colonoscope introduction to caecal intubation.

(7) Duration of the examination

It is defined as the time (expressed in minutes) from caecal intubation to colonoscope withdrawal.

(8) Need of a rescue treatment

"Yes" if a rescue medication was administered and the item "Was any enema needed to achieve preparation?" is "Yes", "No" otherwise.

(9) Need of a nasogastric tube to complete preparation

"Yes" if a nasogastric tube was inserted and the item "Was a nasogastric tube inserted?" is "Yes" at dose 1 or dose 2, "No" otherwise.

(10) Compliance in percentage

The percentage of compliance is defined as (planned volume - residual volume) / planned volume, adding up the solution and water volume where applicable.

50/62

The planned volume is 750 mL for Eziclen (375 mL per dose), 1500 mL for hydration (750 mL per dose) and 70 mL/kg for Klean-Prep® with a maximum of 4000 mL (maximum 2000 mL per dose).

(11) Compliance with the instructions of use

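### The compliance derivation ignores the route of intake, so a subject completed by nasogastric tube can be classed as having drunk everything, which dilutes any between-arm difference in completion by mouth

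*SAP*

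**What the plan says.** One secondary objective (Protocol 2.2.2) is: "To assess compliance with preparation administration in both study arms". Protocol 7.3.2.2 has the subject or caregiver record "residual volumes of preparation (volumes not taken by the subject"), and SAP Appendix 1 item 10 turns that into a percentage: "The percentage of compliance is defined as (planned volume - residual volume) / planned volume". Item 12 cuts the same percentage into classes. For the yes/no version, SAP 3.2.1.2.10 counts a subject as compliant "if he/she drinks the whole preparation (volume = 100" %). Appendix 1 item 11 likewise speaks of drinking and equates it with 100% on the item 10 scale. The percentage is compared between arms by ANOVA, and the yes/no and class versions by CMH.

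The same tube provision applies to both arms. The synopsis and Protocol 6.1.1 say: "If a subject experiences difficulty in drinking the bowel cleansing preparation, a nasogastric tube will be placed". Section 6.1.2 repeats this for Klean-Prep. Section 5.2.2 says "If a subject is unable to complete the preparation, a nasogastric tube will be placed", and its list of procedures says "nasogastric tube may be placed if needed for completion of preparation".

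Tube use is recorded per dose (Appendix 1 item 9) and is a secondary endpoint in its own right (SAP 3.1.2, 3.2.1.2.8). For tolerability, SAP 3.2.2.4 plans that "each symptom after each dose will be summarised by treatment group and use of nasogastric tube (Yes/No"). No such split is planned for compliance or acceptability.

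**The concern.** The SAP's words and its arithmetic describe different things. The words concern drinking; the arithmetic concerns volume left over. The two agree for every subject who takes the preparation by mouth and can part company for a subject who stops drinking and receives the rest by tube. Neither document says whether tube-given volume counts as taken or as residual.

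The gap matters because drinkability is part of the case for the product. Protocol 1.1 describes poor compliance with large-volume regimens, and 1.4 suggests that a smaller volume may make patients more willing to complete the preparation. The subjects who show that difficulty most clearly are the ones a route-blind figure can record as fully compliant.

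**Working it through.** **Plan's own figure.** The documents give no figure for compliance, acceptability or tube use. The only relevant design figure is the arm size. With 85% success in both arms, a 15% margin, one-sided alpha 0.025 and 90% power: n = (1.960 + 1.282)² × 2 × 0.85 × 0.15 / 0.15² = 119.1, so 120 per arm; 120 / 0.96 = 125. This reproduces SAP 1.4.4. It does not bear on the point except to supply n = 125 below.

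**Step 1: one subject under the two readings.** Take a 50 kg Klean-Prep subject (weight assumed). Planned volume is 70 × 50 = 3500 mL. The subject drinks 1750 mL and the other 1750 mL goes by tube.

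- Tube volume counted as taken: residual 0, compliance (3500 − 0) / 3500 = 100%, top class, compliant.
- Tube volume counted as not drunk: residual 1750 mL, compliance (3500 − 1750) / 3500 = 50%, not compliant.

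The SAP does not say which applies. Its formula fits the first and its verb fits the second.

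**Step 2: proportion compliant.** Let m be the share not finishing by mouth and f the share of those brought to full volume by tube. If tube volume counts as taken, reported compliant = 1 − m(1 − f). Assume m = 7% for Eziclen/Izinova (Protocol 1.4 gives at least 93% completion for the one-day adult regimen), m = 20% for Klean-Prep, and the same f in both arms. The reported difference is then 13 × (1 − f) points. Power is two-sided 5%, 125 per arm, normal approximation without country adjustment: Φ{[d − 1.96 √(2p̄(1 − p̄)/n)] / √([p₁(1 − p₁) + p₂(1 − p₂)]/n)}.

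| f | Eziclen/Izinova | Klean-Prep | Difference (points) | Power |
|---|---|---|---|---|
| 0 | 93.0% | 80.0% | 13.0 | 86% |
| 0.25 | 94.75% | 85.0% | 9.75 | 73% |
| 0.5 | 96.5% | 90.0% | 6.5 | 54% |
| 0.75 | 98.25% | 95.0% | 3.25 | 30% |
| 1 | 100% | 100% | 0 | none |

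**Step 3: mean percentage.** Let t be the tube rate and s the share drunk before the tube. If every tubed subject reaches full volume and all others finish by mouth, the reported mean is 100% in both arms. The mean by mouth is 1 − t(1 − s), so the hidden difference is (t_K − t_E)(1 − s). For s from 70% down to 30%:

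- 5% vs 10% tubed: 1.5 to 3.5 points
- 5% vs 20% tubed: 4.5 to 10.5 points
- 10% vs 30% tubed: 6 to 14 points

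**Step 4: what the tube-need endpoint shows.** In the Step 3 setting, needing a tube and not finishing by mouth are the same event, so that endpoint carries the whole contrast. Power with 125 per arm is 32% at 5% vs 10%, 75% at 5% vs 15%, 95% at 5% vs 20% and 98% at 10% vs 30%. With partial tubing the contrast is split. At f = 0.5, with tubes only in those they complete, tube need is 3.5% vs 10% (6.5 points) and compliance shows the other 6.5 points. The two add to 13, but neither analysis reports completion by mouth on its own.

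**The case against.** The strongest reply is that nothing is lost to the reader. SAP 3.2.1.2.8 reports tube need by treatment group with confidence intervals, a country-adjusted CMH test and a table by dose. That stands, and it rules out saying that the trial cannot show the difference. It does depend on the code: the sample program in that section selects Eziclen/Izinova exposure records only. If that variable holds the product received, Klean-Prep subjects drop out, contrary to the section's own text.

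Second, no sentence says that tube volume counts as compliance. That also stands: this is an undefined rule, and how the leaflet or eCRF records tube volume is not in the documents.

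Third, volume delivered by any route is a legitimate exposure measure, and a subject tubed as the protocol provides has not broken it. This stands for the percentage. It does not rescue a yes/no definition worded as drinking.

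A reader might also infer that acceptability is distorted in the same way. The documents do not support that. Acceptability is a five-point rating after each dose, not a volume, and its lowest category can describe a subject who refused. What remains is narrower: the other categories presuppose that the subject took the full dose, and no convention or split covers a dose given by tube.

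Finally, the conditional wording in the 5.2.2 procedures list is largely compatible with the firmer wording elsewhere, so it is weak evidence that tube use will vary by site.

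**Conclusion.** The point holds as a gap in definition with a predictable direction. If tube-given volume is recorded as taken, and similar shares of non-completers are tubed to full volume in both arms, differences in completion by mouth are diluted in the compliance ANOVA and CMH analyses. In the illustration, 13 points become 6.5 at half tubed and 3.25 at three quarters. All non-completion and tube rates here are assumptions; if f differed between arms, the difference would not shrink by one common factor.

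A reader might conclude that both arms must come out at 100%. That needs every non-completer to be tubed to full volume, which the documents do not establish, and the SAP keeps compliance classes down to below 50%.

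The compliance objective is to assess rather than compare, secondary endpoints are tested descriptively (SAP 3.1.5), and the primary analysis is untouched. Importance is low to moderate.

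**What to change.** In SAP 3.2.1.2.10 and Appendix 1 items 10 to 12:

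- State that volume given by nasogastric tube is not volume drunk, and how it is recorded.
- Define compliance with the instructions of use as 100% of planned volume with no tube at dose 1 or dose 2, using the item 9 flag.
- Keep the percentage of volume delivered by any route, labelled as exposure.
- Present percentage and class compliance by treatment group and tube use, as already planned for tolerability.
- Present acceptability ratings descriptively by tube use. Do not recode them: assigning the lowest category to tubed doses would overwrite what the subject or caregiver reported.

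Check the record selection in the 3.2.1.2.8 sample code so that both arms enter the tube-need analysis. Reconcile the protocol passages on when a tube is placed (synopsis, 5.2.2, 6.1.1, 6.1.2), which differ in trigger and in force.

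The cost is SAP wording and a small programming change. The flag-based definition and the tables use data already collected per dose. The price is a somewhat lower stated proportion compliant in any arm where tubes are used.

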- **Prolongation of hospitalisation** is defined as any extension of an in-patient hospitalisation beyond the stay anticipated/required in relation to the original reason for the initial admission, **as determined by the investigator or treating physician**. For protocol-specified hospitalisation in clinical studies, prolongation is defined as any extension beyond the length of stay described in the protocol. Prolongation in the absence of a precipitating, treatment emergent, clinical AE (i.e. not associated with the development of a new AE or worsening of a pre-existing condition) may meet criteria for "seriousness" but is not an adverse experience and thus is not subject to immediate reporting to the sponsor.
- Preplanned or elective treatments/surgical procedures should be noted in the subject's screening documentation. Hospitalisation for a preplanned or elective treatment/surgical procedure should not be reported as an SAE unless there are complications or sequelae which meet the criteria for seriousness described above.

Any SAE must be reported immediately (within 24 hours), independent of the circumstances or suspected cause, if it occurs or comes to the attention of the investigator at any time during the study period.

Any AE/SAE with a suspected causal relationship to IMP administration or comparator occurring at any other time after completion of the study must be promptly reported.

The following information is the minimum that must be provided to the sponsor pharmacovigilance contact within 24 hours for each SAE:

- Study number
- Centre number
- Subject number

PAGE 52/103

- AE
- Investigator's name and contact details

The additional information included in the SAE form must be provided to the sponsor or representative as soon as it is available. The investigator should always provide an assessment of causality for each event reported to the sponsor. Upon receipt of the initial report, the sponsor will ask for the investigator's causality assessment if it was not provided with the initial report.

The investigator should report a diagnosis or a syndrome rather than individual signs or symptoms. The investigator should also try to separate a primary AE considered as the foremost untoward medical occurrence from secondary AEs which occurred as complications.

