# 8.5 Histological examination of colonic biopsy

Should any macroscopic lesions suspected by the investigator to be induced by colonic lavage, the histological examination of the biopsies will be described and recorded as a TEAE.

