Additionally, lesions suspected to be caused by colonic lavage (identified during the potential histological examinations of taken colonic biopsy specimens) will be recorded as AEs with the mention "suspected to be caused by colonic lavage" in the verbatim term by the investigator. The occurrence (Yes/No) of such AEs will be summarised for the treated subjects for whom the colonoscopy was done by treatment group and overall as well as the incidence by SOC/PT. The result of the biopsy will be listed.

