A subject is considered as compliant with the instructions of use if he/she drinks the whole preparation (100% of compliance) and any required further fluid intake (100% of compliance).

The planned volume is 750 mL for Eziclen (375 mL per dose), 1500 mL for hydration (750 mL per dose) and 70 mL/kg for Klean-Prep® with a maximum of 4000 mL (maximum 2000 mL per dose).

(12) Compliance in class

The compliance in class is defined from the compliance in percentage as follows:

- 100 %,
-]100-75],
-]75-50],
- < 50 %.
- (13) Lesions caused by colonic lavage

Histological examination results of lesions caused by colonic lavage will be identified among the adverse events by looking for the term "colonic lavage" in the verbatim term, since the investigator should identified the suspected lesions using "suspected to have been caused by colonic lavage". The occurrence (Yes/no) will then be derived for each subject.

(14) Baseline

Baseline will be derived as the last available assessment before administration of the IMP.

(15) Changes from baseline

Changes from baseline will be calculated as a difference from baseline (e.g. assessment at the visit – assessment at baseline).

(16) Therapeutic Class.

The therapeutic class will correspond to the first 3 digits of the ATC code. The decoding of the therapeutic class will be done from the WHO-DD (current version at the time of database lock).

(17) Prior and concomitant flags

The date of first administration of study treatment (study day 1) is used as the cut-off date for the definition of prior and concomitant medications. A drug started before study day 1 and continuing at time of Day 1 is considered as both, prior and concomitant. Prior, concomitant and both prior and concomitant will be coded as P, C and PC respectively.

(18) Concomitant therapy duration

If times are available, the duration of concomitant treatments will be calculated as (end date/time - start date/time). If at least one time is missing, the duration of concomitant treatments will be calculated as (end date - start date) + 1. If the recorded end date is continuing at the end of the study then the end date will be listed as "ongoing" and the duration will be approximated as " \geq (last attended visit date - start date) + 1" day(s). If the start date or the end date are partial, the duration will be presented as an inequality " \geq xx" day(s) [i.e. \geq 2 where start date=31JAN2004 and end date=FEB2004 or start date=JAN2004

51/62

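### The lavage-lesion safety flag rests only on a free-text match for a phrase the protocol never asks investigators to write, so recorded lesions can be missed in their own table

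*SAP*

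**What the plan says.** Protocol section 3.2.2.2 and SAP section 3.1.3 both list, as a safety variable, the description and histology of biopsied mucosal lesions that the investigator suspects of being due to colonic lavage.

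The protocol's recording instruction is in section 8.5. For such lesions, "the histological examination of the biopsies will be described and recorded as a TEAE". It prescribes no wording for the AE term. Section 8.1.3 requires the investigator to rate causality for every AE in the eCRF.

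SAP section 3.2.2.1 states a labelling convention: the lesions "will be recorded as AEs with the mention 'suspected to be caused by colonic lavage' in the verbatim term by the investigator". It then sets the output: "The occurrence (Yes/No) of such AEs will be summarised for the treated subjects for whom the colonoscopy was done", by arm and overall, together with incidence by SOC and PT. It adds: "The result of the biopsy will be listed".

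SAP Appendix 1, item 13, gives the derivation. Lesions "will be identified among the adverse events by looking for the term 'colonic lavage' in the verbatim term", for this reason: "since the investigator should identified the suspected lesions using 'suspected to have been caused by colonic lavage". Then: "The occurrence (Yes/no) will then be derived for each subject". The item contains no other condition.

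**The concern.** The flag has one input, the free text of the AE term. It does not use the coded PT, the causality rating, the colonoscopy findings or the biopsy result. The phrase it relies on is a convention written in the SAP, whereas investigators work from the protocol, which does not contain that instruction. A lesion can be recorded exactly as protocol section 8.5 asks and still lack the string.

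At stake is the dedicated by-arm table for the only listed endpoint on mucosal injury in adolescents. A zero there would be read as reassurance, and the reader could not tell an absence of lesions from an absence of the phrase. The SAP specifies no step that would tell the two apart before database lock.

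**Working it through.** The plan states no lesion rate and no other figure for this endpoint, so there is nothing to reproduce. The check compares the passages, tries the rule on example terms, and scales one misclassified subject.

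**1. The phrase.** The SAP words it in two ways (*to be caused by* in section 3.2.2.1, *to have been caused by* in Appendix 1). Both contain the search string, so either would be found. In the protocol, *colonic lavage* appears in the name of the safety variable and in section 8.5 as a description of the lesion, not as text to enter in the AE term.

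**2. Neighbouring derivations.** In the same appendix, completion of the procedure (item 5), rescue treatment (item 8) and nasogastric tube (item 9) each use a named yes/no question. Item 13 uses free text alone.

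**3. The rule on example terms.** A case-insensitive search for *colonic lavage* was applied to nine invented terms. They show what the rule does. They do not estimate how often it happens.

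| Invented AE term | Flag |
|---|---|
| Aphthoid erosion suspected to be caused by colonic lavage | Yes |
| Aphthoid erosion suspected to have been caused by colonic lavage | Yes |
| Macroscopic lesion induced by colonic lavage | Yes |
| Aphthoid erosions of sigmoid, histology: focal active colitis | No |
| Mucosal erosion suspected due to bowel preparation | No |
| Lesion suspected caused by colon lavage | No |
| Nausea during colonic lavage | Yes |
| Mucosal lesion not related to colonic lavage | Yes |
| Vomiting after lavage | No |

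The first three use wording found in the documents and are captured. The next three are plausible under protocol section 8.5 and are missed. Of the last three, one is a symptom and one an explicit denial of causality, and both are flagged as lesions. The ninth is correctly not flagged, because *lavage* alone does not match.

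**4. A second route to a miss.** SAP section 3.2.2.6 has colonoscopy findings coded and tabulated separately from AEs. A lesion entered only there cannot be found by searching AE terms.

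**5. Scale of one subject.** Input: 125 randomised per arm (protocol section 10.2). The actual denominator is treated subjects with a colonoscopy, so at most about this. Exact (Clopper-Pearson) 95% intervals, chosen here for illustration:

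- 0/125 = 0%; upper limit 1 − 0.025^(1/125) = 2.9%.
- 1/125 = 0.8%; lower limit 1 − 0.975^(1/125) = 0.02%; upper limit, the 97.5th percentile of Beta(2, 124), = 4.4%.

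One missed lesion is therefore the difference between a table showing none and a table showing 0.8% (0.02% to 4.4%).

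**6. What cannot be computed.** The expected number misclassified is the number of lesions times the proportion of terms without the phrase, plus non-lesion AEs that contain it. None of these quantities is in the documents.

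**The case against.** The strongest reply is that the SAP does state a convention, twice, and that any investigator who follows it is captured. The endpoint is itself defined by the investigator's suspicion, so looking for a written attribution is relevant to it. eCRF guidance or a monitoring manual, not available here, may have carried the phrase to sites. Other outputs also limit the harm. A missed lesion AE rated related would still appear in the TEAE and related-TEAE tables by arm, its biopsy result would be listed, and colonoscopy findings have their own table. A nausea term caught by mistake would show as nausea in the SOC/PT table of flagged events. SAP section 4.3 requires outputs to be cross-checked for consistency.

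Most of this stands, and it limits the point to what can happen. It does not close the gap. The convention is absent from the protocol, no output is said to be reconciled with the flag, and a lesion visible in a general TEAE table does not correct a zero in the dedicated one.

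A reader might infer more than the documents support:

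- *That lesions are in fact missed, or unrelated AEs in fact counted.* Nothing shows that either occurred.
- *That protocol section 8.1.4 steers investigators away from the phrase.* Its sentence, "The investigator should report a diagnosis or a syndrome rather than individual signs or symptoms", sits in the SAE reporting section, contrasts a diagnosis with symptoms, and does not rule out an added attribution. Section 8.5 is the relevant text.
- *That false positives are likely because symptom scores of 2 or more must be reported as AEs (protocol section 8.6).* That makes symptom AEs numerous, but nothing suggests that their terms would mention colonic lavage.
- *That the loss can be stated as a probability of a false zero or as lost power.* This would need invented lesion and compliance rates, and no test between arms is planned for this endpoint.

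**Conclusion.** The concern holds in limited form. The lesion flag depends solely on a free-text match for a phrase that the SAP assumes and the current protocol does not prescribe. It has no link to a documented lesion, a biopsy record or the causality rating. Lesions recorded as the protocol asks can be missed in the dedicated by-arm table. Counting an AE that is not a lesion is possible but less likely.

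The size of the error is not computable from the documents. With few events, one subject decides whether an arm of 125 shows 0% or 0.8%. The conclusion assumes that no site-level instruction outside these documents enforces the phrase; if one does, the risk of a miss is smaller, and a reconciliation would confirm it. The endpoint is descriptive, so the primary analysis, alpha and sample size are untouched.

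**What to change.** Amend SAP Appendix 1, item 13, and section 3.2.2.1 as follows.

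1. Keep the string match, but only as one screening source.
2. Before database lock, produce a treatment-masked listing that sets side by side the string hits, AEs coded to a colonic or rectal mucosal lesion and rated related, colonoscopy findings, and biopsy results.
3. Query the site where the investigator's suspicion is unclear or causality is missing. Missing causality should not count automatically, although SAP section 3.2.2.1 treats it as related for AE summaries. Inclusion criterion 6 admits subjects under surveillance for inflammatory bowel disease, so an erosion from underlying disease could otherwise be counted as a lavage lesion.
4. Set the flag to Yes only when a mucosal lesion is documented and the investigator suspected colonic lavage as its cause. A string hit without a lesion, or a lesion attributed to underlying disease, is No.

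The listing draws on data that the documents say are collected. They show no dedicated field for the investigator's suspicion about a biopsied lesion, which is why queries may be needed. The cost is a short SAP change, one listing and a few masked queries.
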